**Table 1 Schedule of Activities (SoA)**

|              | Screening                   |               | Treatment Period |             |                |             |                |             |                | EDV | Safety Follow-up period   | Final Follow-up Visit | Details in CSP Section or Appendix |
|--------------|-----------------------------|---------------|------------------|-------------|----------------|-------------|----------------|-------------|----------------|-----|---|-----------------------|------------------------------------|
|              | 1                           | 2             | 3                | 4           | 5 a | 6           | 7 a | 8           | 9 a |     |   |                       |                                    |
| Visit Number |                             |               |                  |             |                |             |                |             |                |     | 10, 11 a ,
12, 13 a ,
14, 15 a | 16                    |                                    |
| Study Week   |                             |               | 0                | 1           | 3              | 4           | 6              | 8           | 10             |     | 12, 14,
16, 18,
20, 22  | 24                    |                                    |
| Study Day    | D-42 to
D-1  | D-7 to
D-1 | D1               | D8          | D22            | D29         | D43            | D57         | D71            |     | D85,
D99,
D113,
D127,
D141,
D155                       | D169                  |                                    |
| Visit Window |                             |               |                  | ± 1
days | ± 2
days    | ± 2
days | ± 2
days    | ± 2
days | ± 2
days    |     | ± 2
days   | ± 2
days           |                                    |

Note: Participants are required to fast for at least 8 hours overnight prior to all study visits except for Visit 1; Participants are permitted to drink water during this period of fasting until 1 hour before blood sampling. On days where participants attend the clinic in a fasted state, blood and urine samples should be obtained prior to administration of IP.

Note: Samples to be obtained from all treatment arms unless specified in the table.

- a Home visits: may be undertaken at the participant’s home or any other appropriate location by site staff or by qualified external service provider. Other visits currently not designated as ‘home visits’ may also be undertaken at the participant’s home or any other appropriate location if deemed applicable, following consultation with the Investigator and the sponsor. Home visits performed by qualified external service provider (i.e. not by clinical trial site personnel) may only be performed starting Visit 5 (D22), excluding dosing visits (Visit 6 (D29) and Visit 8 (D57)).
- b Check screening labs and inclusion/exclusion criteria.
- c Weight should be measured in light indoor clothes, without shoes, after a prior visit to the bathroom.
- d Injection Site Reaction assessments to be collected based on adverse event collection criteria.
- e Vital signs and ECG to be measured pre-dose on dosing days.
- f ECG to be performed during the safety follow up period at Visits 10 (D85), 11 (D99), 13 (D127), and 15 (D155).
- g Blood samples for complement activation panel and coagulation parameters will be taken around Cmax and are to be collected pre-dose and 2 hours post-dose.
- h Samples to be obtained pre-dose on dosing days.

**Table 1 Schedule of Activities (SoA)**

|              | Screening                   |               | Treatment Period |             |                |             |                |             |                | EDV | Safety Follow-up period   | Final Follow-up Visit | Details in CSP Section or Appendix |
|--------------|-----------------------------|---------------|------------------|-------------|----------------|-------------|----------------|-------------|----------------|-----|---|-----------------------|------------------------------------|
| Visit Number | 1                           | 2             | 3                | 4           | 5 a | 6           | 7 a | 8           | 9 a |     | 10, 11 a ,
12, 13 a ,
14, 15 a | 16                    |                                    |
| Study Week   |                             |               | 0                | 1           | 3              | 4           | 6              | 8           | 10             |     | 12, 14,
16, 18,
20, 22  | 24                    |                                    |
| Study Day    | D-42 to
D-1 l | D-7 to
D-1 | D1               | D8          | D22            | D29         | D43            | D57         | D71            |     | D85,
D99,
D113,
D127,
D141,
D155                       | D169                  |                                    |
| Visit Window |                             |               |                  | ± 1
days | ± 2
days    | ± 2
days | ± 2
days    | ± 2
days | ± 2
days    |     | ± 2
days   | ± 2
days           |                                    |

i PK sampling to be performed at Visits 4 (D8), 6 (D29), 7 (D43), 8 (D57), 9 (D71), 10 (D85), 12 (D113) and 14 (D141) and final follow-up visit/EDV. Schedule of sampling for Visits 4 (D8), 6 (D29), 8 (D57) are shown below.

Visit 4 (Day 8; Loading dose): pre-dose

Visit 6 (Day 29; Dose 3): pre-dose

Visit 8 (Day 57; Final dose): pre-dose

j ADA sampling to be performed at Visits 3 (D1), 4 (D8), 6 (D29), 8 (D57), 10 (D85), 12 (D113), and 14 (D141), and final follow-up visit/EDV. ADA samples to be collected pre-dose on all dosing days.

k If, for any reason, the sample is not drawn pre-dose on Visit 3 (D1), it may be taken at any visit until the Final follow-up/EDV visit.

l Visit 1 and visit 2 may be combined.

BMI = body mass index; CSP = clinical study protocol; D = day; ECG = electrocardiogram; EDV = early discontinuation visit; HbA1c = haemoglobin A1c; LDL-C = low-density lipoprotein cholesterol; PCSK9 = proprotein convertase subtilisin/kexin type 9; RTSM = Randomization and Trial Supply Management.

## 2. INTRODUCTION

### 2.1 Study Rationale

AZD8233 is a PCSK9-targeted ASO for the reduction of circulating levels of LDL-C. This study aims to evaluate the dose-dependent reduction in LDL-C after SC administration of multiple doses of AZD8233 as well as the associated adverse effects profile. The data generated will be used to guide choice of doses, dosing regimens, and sample sizes, as well as safety and PD monitoring in the further clinical development program.

### 2.2 Background

Dyslipidemia, particularly elevated levels of plasma LDL-C, is a main risk factor for CVD. Hypercholesterolemia is typically caused by a combination of environmental and genetic factors. Statin therapy is the standard lipid lowering medication for both secondary and primary prevention of CVD, as an adjunct to diet. Reduction of LDL-C by statins leads to a significant reduction in cardiovascular events ([Collins R et al 2016](#)). Statins reduce LDL-C by inhibiting HMG-CoA reductase, the rate-limiting enzyme of hepatic cholesterol synthesis. However, despite the substantial benefits of statin therapy, many patients do not reach LDL-C target goals and some continue to be at residual CVD risk despite maximum doses.

Genetic studies have identified PCSK9 as an important, HMG-CoA-independent circulating regulator of LDL-C ([Cohen J et al 2005](#), [Cohen J et al 2006](#)). Gain of function mutations in PCSK9 cause familial hypercholesterolemia; loss of function is associated with low circulating levels of LDL-C and a reduced risk of major vascular events. Molecularly, circulating PCSK9 is derived mainly from the liver and increases LDL-C by promoting degradation of hepatic LDL receptors.

Two monoclonal antibodies (evolocumab [Amgen] and alirocumab [Sanofi/Regeneron]) have been successfully developed to pharmacologically inhibit circulating PCSK9. Injection of these compounds lowers LDL-C levels by approximately 60%, even in clinical study participants already receiving maximum dose statin therapy ([Sabatine MS et al 2017](#), [Ray KK et al 2017](#)). Based on the significant clinical benefit of PCSK9 inhibition, AstraZeneca is developing a PCSK9-targeted, N-acetylgalactosamine-conjugated ASO specifically inhibiting intracellular PCSK9 expression in the liver ([Prakash TP et al 2014](#)). AZD8233 may provide novel treatment options for participants with dyslipidemia.

A detailed description of the chemistry, pharmacology, efficacy, and safety of AZD8233 is provided in the Investigator's Brochure ([Investigator's Brochure 2019](#)).

### 2.3 Benefit/Risk Assessment

Potential risks of AZD8233 and mitigation strategy are shown in [Table 2](#). More detailed

information about the known and expected benefits and potential risks of AZD8233 may be found in the Investigator’s Brochure.

### 2.3.1 Risk Assessment

**Table 2 Risk Assessment**

| Potential Risk of Clinical Significance | Rationale for Risk   | Mitigation Strategy (refer to IB Section 5.5 for further detail)   |
|---|--|--|
| Study Intervention               |  |  |
| Thrombocytopenia                 | Severe thrombocytopenia has been observed in some ASO programs and it is not known whether other members of the class may be affected (Crooke ST et al 2017). One case of severe thrombocytopenia was observed in the non-human primate toxicology study with AZD8233.   | Monitoring of platelet count. In case of severe thrombocytopenia, the action plan detailed in Appendix F will be followed. |
| Acute Kidney Injury              | Kidney is an oligonucleotide high-uptake tissue. Tubular necrosis has been observed with ASOs including an ASO inhibiting PCSK9. This was not observed in toxicological studies with AZD8233 (Van Poelgeest EP et al 2013, Van Poelgeest EP et al 2015, Van Meer L et al 2017).  | Monitoring of S-creatinine, BUN, urine albumin and urine total protein as well as calculation of eGFR.                     |
| Transaminase Elevation           | Liver is an oligonucleotide high-uptake tissue (Hung G et al 2013). Oligonucleotide treatment may cause transient transaminase elevations in mice, monkeys and humans at therapeutic exposures (Burdick AD et al 2014, Hagedorn PH et al 2013, Hildebrandt Eriksen ES et al 2012). AZD8233 is a GalNAc conjugated oligonucleotide, utilizing the ASGP-R to enhance the uptake by hepatocytes. There was however no treatment related histological changes in the liver or changes in liver injury biomarkers | Monitoring a panel of liver safety biomarkers including transaminases.   |

| Potential Risk of Clinical Significance | Rationale for Risk  | Mitigation Strategy (refer to IB Section 5.5 for further detail)  |
|---|---|---|
|   | in the non-clinical toxicology studies.   |   |
| Anti-drug Antibodies             | There is a potential risk for antibody formation. Emergence of ADA has been observed in a proportion of clinical study participants after repeated oligonucleotide treatment, leading to change in PK profile. To date, no apparent association of ADA with loss of efficacy or safety findings have been observed.   | Assessment of ADAs and monitoring for immunogenicity effects (including hypersensitivity reactions and ADA effect on PK/PD). Guidance on the definition of an anaphylactic reaction and the action plan that needs to be followed with regards to ADA sampling is presented in Appendix G . |
| Injection Site Reactions         | As with any exogenous substance, injection site reactions may occur as a response to the SC injection of AZD8233. Possible risks associated with SC administration are redness, swelling, pain, induration, and sometimes infection at the administration site. Although observed for some ASOs, injection site reactions are not generally a clinical problem for newer generation ASOs. | Monitoring for injection site reactions   |
| Complement Activation            | This is a known class effect of oligonucleotides and appears to be directly plasma concentration ( $C_{max}$ ) driven. Monkeys are considered more sensitive to complement activation than humans ( Crooke ST et al 2016 ). No indication of complement activation induced by AZD8233 have been observed in toxicology studies.   | Assessment of complement activation around $C_{max}$ (C3a, C5a, Bb)   |
| Increased Bleeding Risk          | Increases in aPTT, in the absence of clinical or pathological sequelae, have been observed with ASOs ( Burel S et al 2013 , Henry SP et al 1997 ). Mechanistically, interaction of ASOs with the intrinsic tenase complex and thrombin results in a selective inhibition of the intrinsic clotting  | Assessment of aPTT and PT   |

| Potential Risk of Clinical Significance | Rationale for Risk   | Mitigation Strategy (refer to IB Section 5.5 for further detail)  |
|---|--|---|
|   | cascade and hence aPTT ( Henry SP et al 2017 , Sheehan JP, Lan HC 1998 , Sheehan JP, Thao PM 2001 ). Changes in activity of the intrinsic clotting pathway reverse when ASOs are cleared from plasma. Transient prolongation of aPTT has been described in man and was observed to correlate in a linear manner with the C max at the end of infusion ( Sewell KL et al 2002 ). |   |
| Systemic Inflammatory Effects    | Systemic inflammation with flu like symptoms has been seen in some oligonucleotide programs. No indications of systemic inflammatory effects induced by AZD8233 have been seen in the toxicology studies.  | Monitoring for any flu like symptoms and assessment of hsCRP  |
| Study Procedures                 |  |   |
| Subcutaneous Injection           | Pain near the injection site (for 1 or 2 days) is the most common complication of subcutaneous injections.   | Slow injection of AZD8233 using gentle pressure (at least 5 seconds duration is recommended) and rotation of injection sites. |

ADA = anti-drug antibody; aPTT = activated partial thromboplastin time ASGP-R = asialoglycoprotein receptor; ASO = antisense oligonucleotide; BUN = blood urea nitrogen; Cmax = maximum plasma concentration; eGFR = estimated glomerular filtration rate; hsCRP = high sensitivity C reactive protein; PCSK9 = ; PT = prothrombin time; PD = pharmacodynamics; PK = pharmacokinetics; SC = subcutaneous

### **2.3.2 Benefit Assessment**

In a previous single ascending dose study, SC administrations of up to CCI AZD8233 have been well-tolerated with no particular safety findings. Doses of CCI were efficacious in lowering PCSK9 by  $\geq 90\%$  and LDL by up to approximately 70% (Study D7990C00001).

A multiple ascending dose study of AZD8233 is ongoing (Study D7990C00002).

Consequently, AZD8233 is expected to lower circulating PCSK9 in this study in all participants (see Section 4.3). Pharmacologic inhibition of PCSK9 is known to increase the catabolism of LDL-C and reduce circulating LDL-C significantly. Low levels of LDL-C are associated with a monotonically lower risk of incident atherosclerotic CVD events, providing an important clinical benefit to patients with dyslipidemia.

A detailed description of the chemistry, pharmacology, efficacy, and safety of AZD8233 is provided in the Investigator's Brochure.

### **2.3.3 Overall Benefit/Risk Conclusion**

Taking into account the measures taken to minimise risk to the participants of this study, the potential risks identified in association with AZD8233 are justified by the anticipated benefits that may be afforded to participants with dyslipidemia.

### 3. OBJECTIVES AND ENDPOINTS

**Table 3 Objectives and Endpoints**

| Objectives   | Endpoints  |
|--|--|
| Primary   |  |
| 
 
To assess the effect of different doses of AZD8233 on LDL-C versus placebo
 
 | 
 
Absolute change from baseline in log-transformed LDL-C in plasma
 
   |
| Secondary   |  |
| 
 
To assess the effect of different doses of AZD8233 on PCSK9 versus placebo
 
 | 
 
Absolute change from baseline in log-transformed PCSK9 in plasma
 
   |
| 
 
To assess the effect of different doses of AZD8233 on LDL-C versus placebo
 
 | 
 
Percentage change from baseline in levels of LDL-C in plasma
 
   |
| 
 
To assess the effect of AZD8233 on other lipid parameters versus placebo
 
   | 
 
Levels of other lipid parameters including:               
 
- TC
 
- HDL-C
 
- Non-HDL-C
 
- VLDL-C
 
- ApoA1
 
- ApoB
 
- Lp(a)
 
- Triglycerides
 
- Remnants cholesterol
 
 
 
 |
| 
 
To evaluate the PK of AZD8233
 
  | 
 
Plasma parameters: population PK parameters to be reported in a separate report.
 
   |
| 
 
To evaluate the immunogenicity of AZD8233
 
                                  | 
 
Development of ADA and titer (if participants are ADA-positive) during treatment and follow-up
 
   |
| Safety  |  |
| 
 
To assess the safety and tolerability of AZD8233
 
                           | 
 
Safety and tolerability will be evaluated in terms of AEs, vital signs, ECG, and
 
   |

| Objectives  | Endpoints   |
|---|---|
|   | clinical laboratory evaluations including platelet count  |
| Tertiary/Exploratory  |   |
| 
 
To assess lipoprotein profile following SC administration of AZD8233
 
  | 
 
Lipoprotein profile, including particle size and number
 
   |
| 
 
To collect and store blood (plasma) and urine samples for potential future exploratory research aimed at exploring biomarkers involved in PK, PD, safety (including anti-platelet antibodies) and tolerability related to AZD8233 treatment or cardiometabolic diseases
 
 | 
 
Results of potential future exploratory biomarker research may be reported outside this study's CSR
 
 |
| 
 
Optional: To store DNA from blood samples according to each country's local and ethical procedures for future exploratory research into genes/genetic variation that may influence response to treatment.
 
   | 
 
Results of possible future genetic research may be reported outside this study's CSR.
 
               |

AE = adverse event; ADA = anti-drug antibodies; ApoA1 = apolipoprotein A1; ApoB = Apolipoprotein B; CSR = clinical study report; ECG = electrocardiogram; HDL-C = high-density lipoprotein cholesterol; LDL-C = low-density lipoprotein cholesterol; Lp(a) = lipoprotein(a); PCSK9 = proprotein convertase subtilisin/kexin type-9; PD = pharmacodynamics; PK = pharmacokinetics; TC = total cholesterol; VLDL-C = very-low-density lipoprotein cholesterol

## 4. STUDY DESIGN

### 4.1 Overall Design

For an overview of the study design, see [Figure 1](#). For details on treatment given during the study, see [Section 6.1](#).

This is a randomized, parallel, double-blind, placebo-controlled, dose-ranging Phase 2b study in approximately 108 participants with dyslipidemia. The primary objective of the study is to investigate the effect of AZD8233 on LDL-C across different dose levels. The study will be conducted at up to 25 sites in up to 4 countries.

The screening period starts up to 42 days before the randomization visit and ends on Day -1. Some participants routinely come fasting to the clinic. In the event that participants come fasting at their own initiative, sites may choose to combine Visit 1 and Visit 2. In case Visit 1 and Visit 2 are combined, the combined visit must take place between -7 to -1 days prior to randomization. Eligible participants will attend 7 visits during the treatment period and 7 additional visits during the safety follow up period. Eligible participants are randomized across four different treatment arms in a 1:1:1:1 ratio for a 12-week treatment period. The planned treatment arms are AZD8233 **CCI** SC, AZD8233 **CCI** SC, AZD8233 **CCI** SC, and Placebo SC on Days 1, 8, 29, and 57.

This study is double-blind with regards to treatment (AZD8233 or placebo) at each dose level. AZD8233 and placebo will be matched for appearance. Participants randomized to placebo will receive a volume of injection that will not differ substantially from participants on active drug. From randomization, every second visit is planned to be a site visit and the visits in-between may be home visits. Home visits are optional, and all visits could be conducted as on-site visits, if this is preferred. Home visits may be undertaken at the participant's home or any other appropriate location by site staff or qualified external service provider. Other visits that are currently not designated as 'home visits' may also be undertaken at the participant's home or at any other appropriate location if deemed applicable, following consultation with the Investigator and the sponsor. Home visits performed by qualified external service provider (i.e. not by clinical trial site personnel) may only be performed starting Visit 5 (D22), excluding dosing visits (Visit 6 (D29) and Visit 8 (D57)).

After the treatment period, participants will continue in a safety follow up period of 12 weeks (up to 16 weeks post last dose).

For detailed information please refer to the SoA ([Table 1](#)).

### 4.2 Scientific Rationale for Study Design

AstraZeneca is developing AZD8233 for the treatment of dyslipidemia. This study aims to

evaluate the effect of different doses of AZD8233 on LDL-C at steady state to select a therapeutic dose for further clinical development.

The scheduled 12 weeks dosing should be sufficient to reach close to steady state conditions in the tissues at the end of the dosing period (estimated terminal half-life of the full length ASO in plasma is 2-3 weeks). Based on these data and the expected time course for PCSK9 and LDL-C reduction, 12 weeks of dosing is predicted to allow for a robust assessment of safety, tolerability, PK, as well as PCSK9 and LDL-C reduction to guide dose selection for further clinical development of AZD8233.

Dosing and follow up schedule were selected based on the long estimated terminal half-life of the full length AZD8233 ASO in plasma as well as the observed time course for PCSK9 levels to return to baseline after single dose administration in man. Monthly dosing is predicted to result in a low level of fluctuation of PCSK9 levels and tissue exposure during dose intervals.

Dosing in the current study will only start after AZD8233 is concluded safe and tolerable by the Safety Review Committee in Study D7990C00002. The definition of safe and tolerable is that none of the pre-specified safety stopping criteria in Study D7990C00002 have been met.

### 4.3 Justification for Dose

Single SC doses of up to **CCI** AZD8233 have been well tolerated in participants with elevated LDL-C (Study D7990C00001). The doses for the current study have been selected based on observed PCSK9 and LDL-C reduction in the single ascending dose study (D7990C00001) and the predicted PCSK9 and LDL reduction at steady state of the selected doses taking expected accumulation into account for a Q4W dosing regimen that includes a loading dose at Day 8. The mid and high dose, planned to **CC** and **CCI** (Days 1, 8, 29, and 57) were selected to achieve a PCSK9 reduction of around 90% during the dose interval and is expected to result in close to maximum achievable effect in terms of LDL-C reduction, with the aim to show that an increase in dose above the mid dose will not result in a clinically significant further reduction in LDL-C. The low dose, planned to **CCI** (Days 1, 8, 29, and 57) was selected to reach a PCSK9 reduction of below 80% over the entire dose interval and was selected to show that decreasing the dose and PCSK9-reduction to below 80% will lead to a clinically significant lower LDL-C reduction as compared to the mid dose. The mid dose was thus selected to be in the therapeutic dose range. Prior to the start of dosing in the current study, safety data after two repeated doses of AZD8233 **CCI** (in Study D7990C00002) as well as safety and potentially PCSK9 and LDL-cholesterol data after repeated (Days 1, 8, 29, and 57) dosing of AZD8233 **CCI** (Study D7990C00002) will have been evaluated. Based on the results from these cohorts, the planned doses in the current study may be slightly adjusted if needed to achieve the intended PCSK9 and LDL-C reduction. However, the highest dose will not exceed **CCI** (Days 1, 8, 29, and 57), which is the highest dose planned to be evaluated in Study D7990C00002.

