## 9. STATISTICAL CONSIDERATIONS

### 9.1 Statistical Hypotheses

The study hypothesis to test is treatment effect of AZD8233 across different dose levels compared to placebo and compared to each other. The null hypotheses for these tests are that the absolute change in log-transformed LDL-C for AZD8233 at some dose level is equal to the absolute change in log-transformed LDL-C for Placebo or any other dose of AZD8233.

The main statistical test to perform has the null hypothesis that the absolute change in log-transformed LDL-C for AZD8233 **CCI** dose is equal to the absolute change in log-transformed LDL-C for AZD8233 **CCI** dose.

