##### **9.4.2.1 Primary Endpoint(s)**

The primary efficacy endpoint is change from baseline in log-transformed LDL-C at the end of Week 12 which will be fitted using a mixed model for repeated measures.

Comparisons of the change from baseline between the treatment arms will be done using least square mean difference between treatment groups as estimated by the fitted model. All treatment arms will be compared with each other.

For active treatment in the study, the geometric mean ratio will be plotted over time.

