### 4.1.1 MMRM assuming a log-normal distribution

An MMRM will be fitted on log-transformed change from baseline. Log-transformed change from baseline is calculated as the visit value in natural logarithm minus the baseline value in natural logarithm.

The visit statistically tested within the MMRM model is week 12 (day 85). All previous available data on scheduled visits will be used in the model. Fixed factors of the model will be treatment, visit and treatment\*visit interaction. The natural log-transformed baseline value of the outcome variable will be used as a covariate. Visits within subjects will be considered as repeated measurements.

Comparisons derived from the model will be:

- AZD8233 **CCI** versus placebo,
- AZD8233 **CCI** versus placebo
- AZD8233 **CCI** versus placebo
- AZD8233 **CCI** versus AZD8233 **CCI**
- AZD8233 **CCI** versus AZD8233 **CCI**
- AZD8233 **CCI** versus AZD8233 **CCI**

The REML approach will be used for the estimation of the variance and covariance parameters of the linear mixed model; two-sided difference test, with alpha level at 5% will be used for the comparisons and for the t-type confidence interval calculation.

The model will be fitted with an unstructured covariance structure and the Kenward-Roger correction applied to obtain the degrees of freedom.

In case the model will not converge for any reason, the following hierarchical model fitting procedure will be adopted:

1. The MMRM will be fitted using a SP(POW) covariance structure; Visit will be expressed as scheduled visit days to accomplish the variance-covariance matrix estimation.
2. The MMRM will be fitted using a CS covariance structure
3. An ANCOVA model will be used

The reportable results from the model will be:

- The LSmean and their 95% CI for each group for the log-transformed change from baseline
- Back transformed LSmean for each group, which correspond to the estimated relative change from baseline; back transformed LSmean is derived as  $[\text{EXP}(\text{LSmean})]$ .
- 95% CI of the back transformed LSmean for each group; 95% CI of the back transformed LSmeans is derived as  $[\text{EXP}(\text{lower limit of the 95\% CI of the LSmean})]$ ;  $[\text{EXP}(\text{upper limit of the 95\% CI of the LSmean})]$ .
- The geometric mean ratio between active groups and the control group; the ratio is calculated as  $\text{EXP}(\text{of the LSmean of the difference})$

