- The 95% CI of the geometric mean ratio; the 95% CI of the ratio is calculated as  $[\text{EXP}(\text{Lower limit of the 95\% CI of the LSmean of the difference})]$ ;  $[\text{EXP}(\text{Upper limit of the 95\% CI of the LSmean of the difference})]$ .
- P-value of the geometric mean ratio

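### The SAP derives six comparisons but commits to reporting only active-versus-control results, leaving the dose-versus-dose ratios and their CIs without a clear place in the outputs

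*Protocol*

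**What the plan says.** **Aims.** Protocol 4.3 gives two reasons, both about LDL-C, for the choice of doses. The mid and high doses were chosen "with the aim to show that an increase in dose above the mid dose will not result in a clinically significant further reduction". As for the low dose, it was chosen to show that going lower "will lead to a clinically significant lower LDL-C reduction as compared to the mid dose". Neither reason carries a numerical threshold.

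**Hypotheses.** Protocol 9.1 sets nulls under which the change at a given dose "is equal to the absolute change in log-transformed LDL-C for Placebo or any other dose of AZD8233". It then singles out one dose-versus-dose test: "The main statistical test to perform has the null hypothesis that the absolute change in log-transformed LDL-C for AZD8233" at one dose equals that at another (the dose labels are redacted). Protocol 9.4.2.1 adds: "All treatment arms will be compared with each other".

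**SAP comparisons.** Sections 4.1.1 and 4.1.2 each list six comparisons derived from the model, three against placebo and three between AZD8233 doses. For these, a "two-sided difference test, with alpha level at 5% will be used for the comparisons and for the t-type confidence interval calculation".

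**SAP outputs.** The reportable results in 4.1.1 include LS means by group, then "The geometric mean ratio between active groups and the control group", its 95% CI, and the "P-value of the geometric mean ratio". Section 4.1.2 uses the same active-versus-control wording for the LS mean difference in percent change. Section 6 cites the protocol's all-arms sentence and states that the statistical outputs carry only some of the comparisons. It does not say which.

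**The concern.** The list of comparisons and the list of outputs in the same SAP section do not match. A programmer could build tables with all six contrasts, or with three, and cite the SAP for either. On the narrower reading, the main test named in protocol 9.1 would have no reported CI or p-value, and neither would the high-versus-mid and low-versus-mid contrasts behind protocol 4.3.

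The study exists to select a therapeutic dose (protocol 1.1 and 4.2), so these contrasts bear directly on what it can conclude. There is also a secondary risk. A claim of no important further reduction needs an estimate with its uncertainty. If a bare non-significant high-versus-mid test were the only result to hand, it could be taken for a plateau when the data are merely imprecise.

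**Working it through.** **1. Set the passages side by side.** Four arms give 4 × 3 / 2 = 6 pairs: 3 against placebo and 3 between active doses.

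| Place | Active versus active covered? |
|---|---|
| Protocol 4.3 | Needed: high vs mid, low vs mid |
| Protocol 9.1 | Yes; the main test is one such pair |
| Protocol 9.4.2.1 | Yes, all pairs |
| SAP 4.1.1 and 4.1.2, comparisons | Yes, 3 of 6 |
| SAP 4.1.1 and 4.1.2, reportable results | Not named; active versus control only |
| SAP 6 | Unclear; a selection that is not named |

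Six listed comparisons are every pair among four arms (assuming the redacted labels are distinct). The list in 4.1.1 therefore omits nothing, and section 6 cannot be describing that list.

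**2. What the narrower outputs would lose.** The point ratio survives, because (high / placebo) ÷ (mid / placebo) = high / mid. The listed outputs include neither its CI nor its p-value.

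**3. Reproduce the plan's sample size.** Inputs from protocol 9.2: difference 0.33 log, SD 0.30, two-sided 5% t-test, 20 per arm, stated power 90%. By the noncentral t, power at 20 per arm is 92.4%, and the smallest n per arm giving 90% is 19. The stated figure holds, slightly on the safe side.

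**4. Precision of a dose ratio.** Take n = 80/4 = 20 (evaluable) and 108/4 = 27 (randomized) per arm.

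- SE = 0.30 × √(2/n) = 0.0949 (n = 20) or 0.0816 (n = 27).
- Half-width = t(0.975, 2n − 2) × SE = 2.024 × 0.0949 = 0.192, or 2.007 × 0.0816 = 0.164.
- Back-transformed, the observed ratio is multiplied by 0.825 to 1.212, or by 0.849 to 1.178.

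With identical observed means, the CI would still include a further reduction of about 17% (n = 20) or 15% (n = 27).

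**5. Chance that the difference test is non-significant.** For an assumed true further reduction r, δ = −ln(1 − r) and the noncentrality is δ / SE. The last row is the only between-dose difference that the documents give.

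| True further reduction | δ | n = 20 | n = 27 |
|---|---|---|---|
| 10% | 0.105 | 81% | 76% |
| 15% | 0.163 | 61% | 50% |
| 20% | 0.223 | 37% | 24% |
| 25% | 0.288 | 16% | 7% |
| about 28% | 0.33 | 7.6% | 2.2% |

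The documents do not say which of these differences is clinically significant, so the range is shown without choosing one.

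**The case against.** **The estimates are already planned.** The SAP applies t-type CIs to the comparisons without restricting them to placebo, and protocol 9.4.2 has model results back-transformed to geometric mean ratios for interpretation. This largely stands. A reader might infer that the SAP drops the active-versus-active contrasts, and the documents do not support that. They support only that the reportable list does not name them.

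**The departure is declared.** A reader might see an undetected contradiction with protocol 9.4.2.1. Section 6 cites that sentence and openly departs from it, so this is not one. The unresolved conflict is with the SAP's own six-comparison list and with the main test in protocol 9.1.

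**Nobody says that non-significance will be read as a plateau.** This is correct. The plateau aim appears only in the dose rationale, and the primary objective is against placebo. A difference test suits the low-versus-mid aim and the powered dose-versus-dose question. A reader might infer that the trial plans to prove a plateau with a failed difference test, but no text says so. A rule for reading the aim may also sit in the separate PK/PD analysis plan (protocol 9.4.2.2) or in the charters (SAP 1.1), which are not available here.

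**The risk of misreading depends on the effect size.** This stands too. At 0.33 log a non-significant result is unlikely, so the risk concerns the smaller differences.

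**Conclusion.** The reporting gap is real and minor. SAP 4.1.1 and 4.1.2 derive six comparisons but promise ratios or differences, CIs and p-values only against control, and section 6 leaves the selection unnamed. Read literally, that omits the CI and p-value for the protocol's main test and for the contrasts behind protocol 4.3.

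The plateau issue is secondary. A non-significant high-versus-mid test would be weak evidence of no further reduction if the true difference were 10% to 15% (non-significant 50% to 81% of the time). It would be much more informative near 25% or above (16% or less).

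These figures assume an unadjusted two-sample t-test, SD 0.30 and 20 or 27 per arm. The baseline-adjusted MMRM may be more precise. Because the dose labels are redacted, it cannot be confirmed which pair the 0.33 difference or the main test refers to.

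**What to change.** 1. **LDL-C outputs.** In SAP 4.1.1 and 4.2.4.1, require the Week 12 geometric mean ratio with 95% CI and p-value for every active-versus-active pair for LDL-C. In 4.1.2, require the corresponding LS mean difference with 95% CI for percent change in LDL-C.
2. **Other lipids.** Section 4.1.2 also serves nine other lipid parameters, so three more pairs each would add 9 × 3 = 27 unadjusted p-values. For these, give estimates and CIs only, or label the p-values nominal.
3. **Section 6.** Delete the sentence limiting output to a selection of comparisons, or name the omitted comparisons and the reason.
4. **Secondary.** Add one sentence that the protocol 4.3 aim of no clinically significant further reduction above the mid dose is read descriptively from the high-versus-mid estimate and 95% CI, not from a non-significant difference test.

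The cost is SAP wording and up to three extra rows per table, from models already planned. No new data or participants are needed. The downsides are some extra unadjusted comparisons and a CI that may leave the plateau question open, which the report would then have to say.
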